Five to 10 hours prior to the dive start time, subjects will be given a telemetric pill to swallow prior to testing. The telemetric pill will be used to measure pre- and post-dive core temperatures in the divers. If the subjects do not swallow the core temperature pill, they will be asked to insert the pill as a suppository the morning of testing. Prior to the dive, subjects will have 21 mL of venous blood drawn. After, subjects will perform dives to depths up to 30 meters and lasting up to 75 minutes with decompression profiles determined using V-planner software according to the varying permeability model (~1.25 hrs). The Dive Master will ensure that all divers have a 'dive buddy', a SCUBA-certified individual of similar or greater experience than the subject. The subject will be encouraged to identify a 'dive buddy' to accompany them, but in the event that the subject is unable to secure a 'dive buddy', the Dive Master will ensure that the subject has a 'dive buddy' for the dive. Subjects will utilize SCUBA equipment owned and maintained by the Croatian Navy.

Subjects will ingest a placebo or sildenafil (50 mg oral) upon resurfacing and coming aboard dry land. During the hour wait until peak effect, the subjects will be instrumented with forehead oxygen saturation monitor, ECG, and blood pressure cuffs. Pulmonary artery pressure, cardiac output and right and left heart function will also be measured using ultrasound. In addition, a post-dive venous blood draw of 21 mL will be taken. This blood draw will occur 1 hour after placebo or sildenafil administration. (~1.5 hrs).

Description of Data Collection Procedures

- **Comprehensive ultrasound screening** (Day 1 for Breath Hold and SCUBA divers):

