- **Intravenous Catheter (IV) and blood draw** (Days 1 & 2 for Breath Hold and SCUBA divers): We will place a 20-22 gauge (small diameter) IV into a vein in the subject's arm that will be used for the rapid injection of the agitated sterile saline for TTSCE. This catheter will also be used to measure serum inflammatory mediators. Blood will be centrifuged and de-identified serum stored at -80°C until assayed by ELISA kit. For the breath hold dive arms, blood will be drawn once on the first visit pre-breath hold (21 mL). For the SCUBA arm, blood will be drawn pre- and post-dive for both visits (21 mL per blood draw x4 blood draws). Total IV blood draw is therefore approximately 84 mL for SCUBA subjects.

- **Breathing low oxygen and high carbon dioxide** (hypercapnic hypoxia) to mimic breath hold (Days 1 & 2, breath hold and breath hold control subjects only):

Subjects will take either sildenafil or a placebo, and will be instrumented during the ~1 hour wait till peak effect. After being instrumented with ECG, forehead saturation and blood pressure monitoring equipment, subjects will breathe room air for 5-10 minutes to measure baseline breathing. During the first 5 minutes of the hypercapnic hypoxic conditions, subjects will breathe room air through a 2-way non-rebreathing Hans Rudolph mouthpiece. During the resting period end tidal (expired) Oxygen will be clamped at 100 mm Hg, while end tidal (expired) carbon dioxide will be maintained at resting levels (~30-40 mm Hg). Upon completion of the baseline measurements, end tidal carbon dioxide will be increased while end tidal oxygen will be reduced.

The values for oxygen and carbon dioxide for breath hold divers will be changed to 45-50 mm Hg CO2 and 50-60 mm Hg O2 and held at this level for approximately 5 minutes while ultrasound measures are made, then subsequently changed to 55-60 mm Hg CO2 and 30-40 mm Hg O2 and held at this level for approximately 5 minutes, while ultrasound measures are made. These values of oxygen and carbon dioxide were chosen based on previous values published in breath hold divers by my collaborating investigator [name] (Willie et al., J Cereb Blood Flow & Metab 2015).

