The values for oxygen and carbon dioxide for breath hold diver controls will be changed to 45-50 mm Hg CO2 and 60-70 mm Hg O2 and held at this level for approximately 5 minutes while ultrasound measures are made, then subsequently changed to 55-60 mm Hg CO2 and 40-50 mm Hg O2 and held at this level for approximately 5 minutes, while ultrasound measures are made. The values used for controls are based off of previous work by our group at altitude (Elliott et al., J Appl Physiol 2015). End tidal oxygen and carbon dioxide levels will be maintained using an end-tidal forcing (ETF) system, (Airforce, Endtidal Forcing System), (Querido et al., 2013; Bain et al., 2013; Foster et al., 2014). (~30 minutes for breathing gases and 1 hour of wait time for drug plasma levels to peak).

- **SCUBA diving** (Days 1 & 2, SCUBA subjects only): Subjects will perform dives to depths up to 30 meters and lasting up to 75 minutes with decompression profiles determined using V-planner software according to the varying permeability model. Subjects will be highly experienced divers. The Dive Master will ensure that all divers have a 'dive buddy', a SCUBA-certified individual of similar or greater experience than the subject.

The subject will be encouraged to identify a 'dive buddy' to accompany them, but in the event that the subject is unable to secure a 'dive buddy', the Dive Master will ensure that the subject has a 'dive buddy' for the dive. A 'Dive Buddy' will be required to provide evidence of appropriate SCUBA certification and ensure that they have not completed a recent dive. Subjects will ingest a placebo or sildenafil (50 mg oral) upon resurfacing and coming aboard dry land. During the hour wait until peak effect, the subjects will be instrumented with forehead saturation, ECG and blood pressure cuffs (~1.5 hrs).

Core Temperature: Core temperature (Tcore) will be measured using a Vital Sense Monitor and a telemetric pill (JonahTM ingestible temperature sensor, Mini Mitter Inc, Bend OR). The sterile telemetric pill will be activated by study staff then will be taken orally (with liquid) the 5-10 hours prior to testing or the volunteer will self-insert the pill into the rectum the morning of testing.

D. Research Population & Recruitment Methods & Compensation

Sample size, Population and Recruitment Methods:

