Mixed saline (saltwater), either alone or with 5% sugar in water **has been used to help see the ultrasound pictures (echocardiogram) for over thirty years.** Saline contrast bubble injections are routinely used to screen for the presence of a patent foramen ovale in the clinic. The American Society of Echocardiography Guidelines (2014) state that "...life threatening reactions are rare (<1 in 10,000)" when using contrast injections (including bubbles with protein shells) and The European Association of Echocardiography (2009) has stated that "... the evidence shows that contrast echocardiography is very safe in clinical practice." And this includes using stabilized bubbles with protein shells and we only use non-stabilized saline contrast bubbles in our lab. We only use a small amount of air mixed with saline, thus the **probability** of any **severe adverse reaction** is very low. Given the evidence presented above, the **probability** of the adverse reactions discussed above is low. Although the **severity** of arterial gas emboli is high, given the amount of air used and the short life span of intravascular bubbles of this size, the likelihood of the constellation of unfortunate events required for a serious adverse reaction to occur is very small.

Breathing low oxygen (hypoxia) and high carbon dioxide (hypercapnia): Risks associated with exposure to hypoxia or hypercapnia during rest include headache, nausea, fatigue, dizziness and shortness of breath and the remote possibility of central nervous system impairment, insomnia, pulmonary and cerebral edema, and death. Subjects will be monitored with an electrocardiogram and peripheral estimate of arterial oxygen saturation using a forehead monitor. Exposure to hypoxia at rest will be brief to minimize the impact of low oxygen. The principal investigator has extensive experience conducting exercise tests with subjects breathing hypoxic gas mixtures in a research setting (Amann, Eldridge et al., 2006; Romer, Havercamp et al., 2007; [name] 2007; [name], Romer, et al., 2008; [name] et al., 2011; Laurie et al., 2010; Elliott et al., 2015). Although the severity of risks breathing hypoxic and hypercapnic gas is potentially high, given the

short duration of exposure and careful monitoring by the research team, the likelihood of a serious adverse event to occur is very small.

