Risks associated with core temperature pill: The risks of using the temperature pills include mechanical injury to the mucus membranes if adequate care is not used. Risks of the temperature pill will be minimized by explaining the procedures to the volunteers. Additionally, ample lubricant (suppository) or water (oral) will be provided to the volunteer. Volunteers with history of obstructive diseases of the gastrointestinal tract including diverticulosis, diverticulitis, inflammatory bowel disease, peptic ulcer disease, Crohn's disease, ulcerative colitis, or previous GI surgery will not use a telemetric pill. These risks only apply to subjects in the SCUBA arm.

Risks for subjects undergoing SCUBA diving: During the research, examinees will dive once to a max depth of 30 meters. Dive time will be a max of 75 minutes. At 30 meters (100 feet), the maximum bottom time before decompression limits are reached is 20 minutes (PADI dive table). When decompression limits are reached or exceeded, a decompression stop on the reascent is needed. Divers can safely exceed recreational decompression limits by adding a decompression stop, as decompression stops are designed to greatly minimize the risks of decompression sickness. Dive computers will be used so subjects can monitor how long they can stay at their current depth before requiring a decompression stop and determine length of a required decompression stop (standardized diving protocol determined by diving computer Galileo, Uwatec). The dive will be done in the presence of a safety diver, a paramedics doctor, while the doctors working at the Institute for hyperbaric medicine will be thoroughly informed about the diving protocol and schedule. Divers will utilize SCUBA equipment owned and maintained by the Croatian Navy. During the dive, the following adverse events are possible:

1. Decompression sickness – a condition in which air bubbles dissolved in tissues suddenly become released into bloodstream due to the decrease of the ambient pressure. Common symptoms include pain in the joints, extremities, dizziness, nausea, vomiting, extreme tiredness, paralysis, collapse and fainting. The incidence of decompression sickness among divers is generally low, ranging from 0.013% to 1.25%. Decompression sickness is primarily related to the depth and duration of the dive, as well as to the duration of decompression while resurfacing.

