2. Arterial gas embolization – the bubbles can reach arterial system in people with defects in the interatrial wall of the heart.
3. Embolization – during the quick decompression, bubbles of oxygen can move from tissues into circulation.
4. Expansion lung injury and pneumomediastinum – can happen during the breath hold while resurfacing.
5. Oxygen narcosis – as a result of toxic effects of high oxygen pressure on nerve conducting, symptoms comparable to drunkenness may happen.
6. Oxygen toxicity – toxic effects of oxygen can be caused by the high quantity of absorbed oxygen, and can present as burning sensations in lungs, spasms, dizziness and vomiting.

Because we will be working with experienced divers utilizing equipment owned and maintained by the Croatian Navy, the probability of these risks is very low, although the severity is moderate.

Sildenafil (Viagra): Adverse reactions previously observed in individuals taking Sildenafil include moderate hypotension, light headedness, dizziness, priapism, sensitivity to light and potential visual disturbances. These reactions are extremely rare and largely associated with individuals who are using Sildenafil for the management of erectile dysfunction or pulmonary artery hypertension. We will further minimize these risks by using healthy subjects with no previous history of cardiovascular disease and use a standard clinical dose of 50 mg P.O. We will also exclude subjects from participation during Stage #1 if they report currently taking specific contraindicated medications (outlined in the exclusion criteria in Table 1). [name], MD, Dr.

[name], and colleagues will be monitoring the subjects and ensuring the subject is not suffering from any negative side effects. Thus, the probability and severity of these risks is very low.

Safety Equipment available in the Laboratory of [name] in the department of integrative physiology at the University of Split School of Medicine in Split Croatia (where testing and screening will be performed) and the laboratory of [name] in the department of human physiology at the University of Oregon: An AED, a spare AED battery and spare AED pads, bottled oxygen and face masks. A standard first aid kit is also available.

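### The risk section says SCUBA subjects dive once, but the plan schedules two dives each, so it states half the planned dive exposure

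*Combined protocol and SAP*

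**What the plan says.** **Number of dives.** Section G, under the risks for SCUBA subjects, states: "During the research, examinees will dive once to a max depth of 30 meters". Section C describes two. Both visit overviews for the SCUBA arm include a dive. The Visit 2 details, following a blood draw, read "After, subjects will perform dives to depths up to 30 meters and lasting up to 75 minutes". The procedure entry for SCUBA diving is labelled "Days 1 & 2, SCUBA subjects only): Subjects will perform dives to depths up to 30 meters". The blood-draw entry says "For the SCUBA arm, blood will be drawn pre- and post-dive for both visits", with four draws of 21 mL and a total of about 84 mL. The compensation text in section D pays for a dive at each visit.

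**Incidence.** Item 1 of the dive-risk list says: "The incidence of decompression sickness among divers is generally low, ranging from 0.013% to 1.25" percent. It does not say whether this is per dive or per diver.

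**Severity.** The list has six hazards. Item 2 is arterial gas embolization, where "the bubbles can reach arterial system in people with defects in the interatrial wall of the heart". After the sixth item, one sentence covers them all: "the probability of these risks is very low, although the severity is moderate". Earlier in section G, under saline contrast echocardiography, the severity "of arterial gas emboli is high".

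**PFO status.** The design summary in section C plans 50 SCUBA divers, 25 of them PFO+. The sample size text in section D gives 12-13 PFO+ per sex. SCUBA Visit 1 runs in this order: consent, contrast screen that grades PFO flow, lung function tests, dive.

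**The concern.** Section G is where participant risk is set out, and the dive is a main source of that risk in this arm. A reader who relies on that section would judge the risk of one dive when two are planned. Section E has staff explain probability and severity to subjects from the consent form, so the count and the ratings behind that form should be right.

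The severity rating is a smaller matter of the same kind. Half of the arm is chosen to have the interatrial opening that item 2 names as the route to arterial embolization. For those subjects, a single rating spread over six hazards is least informative where it matters most.

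The Visit 1 outline also raises a question. Consent is given before the PFO screen, and the outline has no entry for telling the subject the result before the dive that follows.

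**Working it through.** **1. Count the scheduled dives.**
- Risk section: 1 dive per subject.
- Visit schedule: 1 (Visit 1) + 1 (Visit 2) = 2 dives per subject.
- Cross-check on blood: 2 dives × 2 draws (before and after) × 21 mL = 84 mL, which reproduces the plan's total. One dive would give 1 × 2 × 21 = 42 mL.
- Cross-check on payment: $30 + $20 = $50, and 220 + 110 = 330 HRK. Both match the stated maxima, and each visit's amount includes $20 for the dive.

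The plan's own figures reproduce with two dives. The single-dive statement does not fit them. Reading it as once per visit does not work either, since its opening words cover the whole of the research.

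**2. Exposure in the arm, assuming full enrolment.**
- All SCUBA subjects: 50 × 2 = 100 subject-dives, against 50 × 1 = 50 as the risk section implies.
- PFO+ subjects: 25 × 2 = 50. With 12-13 per sex there are 24 to 26 subjects, giving 48 to 52 dives.

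This step needs no incidence figure.

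**3. Decompression sickness under each reading of the range.** Let p be the stated incidence.

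If p is per dive and dives are independent, the risk per subject over two dives is 1 − (1 − p)²:
- p = 0.00013: 1 − 0.99987² = 0.00026, or 0.026% (about 1 in 3,846).
- p = 0.0125: 1 − 0.9875² = 0.02484, or 2.48% (about 1 in 40).
- Expected cases in the arm: 100 × p = 0.013 to 1.25, against 50 × p = 0.0065 to 0.625 for one dive each.

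If p is per diver, the risk per subject stays at 0.013% to 1.25%, and expected cases stay at 50 × p = 0.0065 to 0.625.

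**4. Severity ratings side by side.** In the contrast text, the small volume of air and the short life of the bubbles are reasons why an event is unlikely. In the dive text, experienced divers and well-maintained equipment are again reasons why an event is unlikely. Neither set of reasons bears on how serious an arterial embolus is once it occurs, and nothing in the plan explains why it would be less serious after a dive. No rate is given for arterial gas embolization or for PFO+ divers, so this point cannot be quantified.

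**The case against.** The strongest reply is that the dive count is a drafting slip. Every operative part of section C gives two dives, and nobody running the study would schedule one. Section E has staff explain the whole study verbally before signature. A reader might infer that subjects were told of only one dive. The documents do not show that: the consent form is not in the supplied text, and nothing indicates that it repeats the slip. This part of the reply stands. The figure in the risk section is still wrong.

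On severity, the moderate rating is one summary for six hazards and never rates item 2 by itself, and the high rating belongs to another procedure. It is therefore too strong to say that the plan rates dive embolism as moderate in its own right. What remains is a loose collective label that covers an event rated high elsewhere, with no reason given for the difference.

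On the PFO result, a reader might infer that subjects dive without being told. That rests on silence in a compressed outline, while the likeliest place for such a commitment, the consent form, was not available. The outline is also not a complete timed sequence: the temperature pill is listed after consent yet given five to ten hours before the dive, in a visit of about five hours. The compensation text allows for exclusion on findings at Visit 1, so acting on screening results before the dive is contemplated. General safeguards exist too: cardiac screening, planned decompression profiles, a safety diver, a doctor and a dive buddy. None of these is a disclosure step, but together with the missing form they rule out calling this a shown omission.

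**Conclusion.** The dive count in section G is wrong by the plan's own text. It gives one dive where two are scheduled, and so half the planned exposure: up to 100 subject-dives at full enrolment instead of 50, with 48 to 52 by PFO+ subjects. This conclusion depends only on the visit schedule and the planned numbers.

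A reader might go further and say that the decompression sickness risk is understated by half. The documents do not support that, because the wording may mean a rate per diver, in which case the figure does not change. The 0.026% to 2.48% range holds only if the rate is per dive and dives are independent.

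The severity wording is a lesser inconsistency worth correcting alongside. The disclosure step is a suggestion only. The priority is minor: sample size, power, error rates and analysis are untouched.

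**What to change.** 1. In the SCUBA risk text of section G, say that subjects dive twice, once per visit. State whether 0.013% to 1.25% is per dive (two-dive risk about 0.026% to 2.48%) or per diver (unchanged).
2. In the summary after the six dive hazards, rate arterial gas embolization separately as high severity, in line with the contrast text. Note that item 2 applies to the half of the arm that is PFO+ by design.
3. As a safeguard, add a line to the SCUBA Visit 1 details after the contrast screen: the subject is told the PFO result and what it means for diving, and reconfirms willingness before the first dive.
4. Check that the consent form agrees on all three.

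Items 1 and 2 cost only wording. Item 3 costs a short conversation, with no new procedure or visit. Its downside is that some PFO+ subjects may decline to dive. That would slow filling of the PFO+ quota and could leave a self-selected PFO+ group, which bears on the comparison by PFO status in objectives 4 and 5. Declines after disclosure should therefore be counted and reported.

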
Men and women aged 18-65 recruited from patients in the surrounding Split Croatia community who are elite breath hold divers and highly experienced SCUBA divers, and or age, sex and PFO-matched controls from the surrounding Split Croatia area and the surrounding Eugene/Springfield area for breath hold dive studies only.
	
Previous history of coronary artery disease (ischemic heart disease such as angina, heart attack, myocardial infarction). Currently taking medications or herbal supplements for any heart or respiratory disease that they cannot stop taking for 48hrs prior to testing (seasonal allergy medication not included in exclusion medications). Anyone who is pregnant or trying to become pregnant. Individuals taking Sildenafil or products similar to Sildenafil, such as Tadalafil (Cialis) and Vardenafil (Levitra/Staxyn). Individuals taking NITRATES and other Nitric Oxide donors. If subjects can refrain from using PDE-5 inhibitors for 48 hours before each study day then they will be allowed to participate.
 
Previous history of any condition that would prevent the subject from breathing low oxygen and high carbon dioxide mixtures that mimic a breath hold. (breath hold diving subjects only).
 
Previous history of any condition that would prevent the subject from performing a SCUBA dive. (SCUBA diving subjects only).
 
Control breath-hold dive subjects can't have previous breath hold diving experience
 
Subjects will be excluded from telemetric pill ONLY if they have a history of obstructive diseases of the gastrointestinal tract including diverticulosis, diverticulitis, inflammatory bowel disease, peptic ulcer disease, Crohn's disease, ulcerative colitis, or previous GI surgery.

2. Detailed Recruitment information:

Breath hold divers, controls and experienced SCUBA divers will be recruited using existing contact information by our collaborators in Split. Some control subjects for the breath-hold arm of the study (NOT SCUBA DIVING arm) will be recruited from the Eugene/Springfield area. Additionally, subjects will be provided information about the opportunity to participate in this research by word of mouth and announcements by coaches and affiliated diving personnel associated with this select group of individuals. Breath-hold control subjects will be informally recruited by word of mouth and announcements by coaches

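### Table 1 does not carry the no-cardiovascular-history condition that Section G gives as one ground for rating sildenafil risk very low

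*Combined protocol and SAP*

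**What the plan says.** **Section G, sildenafil paragraph.** The plan lists possible reactions, among them moderate hypotension, and calls them extremely rare. It then says the risk will be reduced further by "using healthy subjects with no previous history of cardiovascular disease" and by using a standard 50 mg dose. It also says staff will "exclude subjects from participation during Stage #1 if they report currently taking specific contraindicated medications (outlined in the exclusion criteria in Table 1"). Subjects will be monitored. From these grounds together it rates probability and severity as very low.

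**Section D, Table 1.**
- Inclusion opens with "Men and women aged 18-65 recruited from patients in the surrounding Split Croatia community who are elite breath hold divers" and goes on to SCUBA divers and matched controls. It has no requirement to be healthy or free of cardiovascular disease.
- The cardiovascular diagnosis excluded by name is "Previous history of coronary artery disease (ischemic heart disease such as angina, heart attack, myocardial infarction").
- The medication clause excludes those "Currently taking medications or herbal supplements for any heart or respiratory disease that they cannot stop taking for 48hrs prior to testing".
- Nitrate and nitric oxide donor users are excluded. For PDE-5 inhibitors there is a worded exception: "If subjects can refrain from using PDE-5 inhibitors for 48 hours before each study day then they will be allowed to participate".
- Two general clauses exclude conditions that would prevent breathing the gas mixtures or performing a dive.

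**Section D item 3.** Before the first visit, each participant is asked about health history and medications, and anyone meeting a Table 1 exclusion is not enrolled.

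**The concern.** Section G describes a population with no cardiovascular history of any kind. The list that staff are told to apply removes only part of that history. Someone with, for example, a past arrhythmia or treated hypertension could pass every Table 1 line and still fall outside the population that Section G assumes.

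That person would receive 50 mg of a vasodilator. In the breath-hold and control groups, hypercapnic hypoxia follows about an hour later. In the SCUBA group, the dose comes on return to land after a dive. One stated reason for the very low rating would not hold for that person. Section H says the study will not improve subjects' health, so the stated basis for the risk should match who can be enrolled.

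**Working it through.** No sample-size, power or alpha figure is involved, so the check compares the two texts and runs illustrative cases through Table 1. The cases are examples, not people described in the documents.

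**Step 1: the two conditions.**
- Section G: no previous cardiovascular disease.
- Table 1: no coronary disease, and any heart medication can be stopped for 48 hours.

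The first is the stricter condition. Meeting the second does not guarantee the first.

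**Step 2: cases.**
- *Previous myocardial infarction.* Excluded by both.
- *Non-coronary heart disease on a drug that cannot be paused.* Excluded by both, through the medication clause in Table 1.
- *Non-coronary heart disease on a drug that can be paused for 48 hours.* Excluded by Section G. No diagnosis line in Table 1 reaches it, and the medication clause does not exclude it.
- *Past non-coronary disease, now untreated.* Excluded by Section G. Neither the diagnosis line nor the medication clause in Table 1 reaches it.
- *Controlled mild hypertension.* Depends on whether the sponsor counts it as cardiovascular disease. Neither text says.

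**Step 3: other safeguards.**
- *Cardiac screening at Visit 1 (Section C).* It looks for abnormalities before dosing, but no exclusion rule for past history is attached.
- *Exclusion on visit findings.* This appears only in the Visit 1 compensation text (Section D item 4), and the findings are not defined.
- *The two general clauses in Table 1.* They test fitness for the gas mixtures or the dive, not for sildenafil. The gas clause is marked for breath-hold diving subjects only, so it is unclear whether it covers the controls.
- *Nitrate exclusion.* It removes users of one contraindicated drug class, not a disease history.
- *Monitoring (Section G).* It responds to events after enrolment.

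Each of these narrows the gap. None states an exclusion for non-coronary cardiovascular history.

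**Step 4: who is exposed.**
- Planned recruitment (Section C): 40 breath-hold divers + 40 controls + 50 SCUBA divers = 130. Section D item 1 agrees: 20 + 20 + 20 + 20 + 25 + 25 = 130.
- PFO+ by design (Section C): 20 + 20 + 25 = 65, and 65/130 = 50%. A bare cardiovascular exclusion could be read as removing these subjects, so any added line needs a PFO exception.
- The documents give no prevalence of non-coronary cardiovascular disease in these groups, so the number affected cannot be calculated.

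**The case against.** The strongest reply is that Section G is part of the same plan and is itself a commitment about whom to enrol. Section D item 3 says that people meeting Table 1 criteria are excluded; it does not say that Table 1 is the only ground. Visit 1 includes a health-history questionnaire and a cardiac screen before dosing, and the questionnaire's content is not in the text available here. All of this stands. A reader might infer that the plan has no rule at all on non-coronary history, but the documents do not support that. The condition is stated; it is missing from the list used at screening.

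Three other strong readings also fail.
- *That the very low rating collapses.* Section G first calls the reactions extremely rare, then adds dose, medication exclusions and monitoring. The history condition is one ground among several.
- *That the 48-hour clause grants entry to people with heart disease.* In words, Table 1 grants entry only to PDE-5 users who pause. The heart-medication clause merely fails to exclude those who can pause.
- *That every other selection safeguard in Section G reaches Table 1 intact.* The gastrointestinal history does ("Subjects will be excluded from telemetric pill ONLY if they have a history of obstructive diseases of the gastrointestinal tract"), but it governs use of one device, not entry. Section G speaks of excluding people who report taking contraindicated drugs, whereas Table 1 lets PDE-5 users in if they pause. No tally of safeguards is relied on here.

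What the reply leaves untouched is that staff working from Table 1 have no line there for this condition, and Section G's pointer to Table 1 covers medications only.

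**Conclusion.** The inconsistency is real and minor. The plan is wrong as written only in that Table 1 does not carry the condition stated in Section G. Applied as written, Table 1 could admit a person whom Section G says will not be enrolled, and that person would take sildenafil with hypercapnic hypoxia or after a dive.

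The number affected among up to 130 subjects is unknown. It is probably small, given that the divers are elite or highly experienced and that other screening steps apply. No endpoint, power or analysis figure changes.

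The conclusion assumes that screening staff work from Table 1, as Section D item 3 directs, and that the cardiovascular wording in Section G means more than coronary disease, as its plain sense suggests.

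**What to change.** Add to the Table 1 exclusions, for all groups: *previous history of cardiovascular disease (isolated PFO permitted)*. State whether controlled mild hypertension counts. Apply the line at the health-history questioning that Section D item 3 already requires before the first visit.

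If the sponsor does intend to enrol people with non-coronary cardiovascular disease, leave Table 1 as it is and reword the Section G ground to match. Either change makes the two texts agree. The 48-hour medication clause needs no separate edit, because a history exclusion would already cover people treated for heart disease.

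The cost is one line in a table, or one reworded sentence, with no new visit or procedure. The added exclusion may lose a few eligible subjects from a small pool of elite divers.
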